3. STUDY DESIGN

3.1. Overview

This is a 2-phase randomized withdrawal study to evaluate efficacy, safety and tolerability, and pharmacokinetics of tofacitinib as a treatment for sJIA. The study will enroll approximately 100 subjects from 2 to <18 years of age with sJIA with active systemic features, defined by either:

- Documented intermittently spiking temperature $>38^{\circ}\text{C}/100.4^{\circ}\text{F}$ due to sJIA for at least 1 day in the screening period and within 1 week before the first dose, and

presence of at least 2 joints with active arthritis at screening and baseline, and ESR
>30 mm/hr [1.5 X ULN] at screening;

OR

- Presence of at least 5 joints with active arthritis at screening and baseline, and ESR
>30 mm/hr [1.5 X ULN] at screening.

The study will target enrollment of at least 12 subjects in the following age groups: from 12 to <18 years, from 6 <12 years, and from 2 to <6 years.

The study will conclude when the requisite number of flares are achieved during the double-blind phase of the study as described in Section 11, Data Analysis/Statistical Methods.

Subjects will be enrolled into an open-label phase during which they will receive tofacitinib 5 mg BID oral tablets, or an equivalent weight-based lower dose of tofacitinib oral solution (1 mg/mL) BID for subjects <40 kg. The 5 mg BID dose level of tofacitinib will be evaluated in a staggered fashion (cohorts of subjects followed by safety review), as described under “Dose Selection” in [Section 3.4](#).

The open-label phase will be divided into two parts. In Part 1, all subjects must achieve and maintain a protocol defined minimum level of clinical response for at least 4 weeks. In Part 2 of the open-label phase, subjects treated with background CSs >0.2 mg/kg/day oral prednisone (or equivalent) will attempt to have their CS dose tapered to a predetermined target range, or lower; subjects who successfully taper their CS dose while maintaining the defined clinical response, will be eligible for the double-blind withdrawal phase of the study. The minimum total duration of treatment with a stable dose of tofacitinib for subjects completing Parts 1 and 2 must be 12 weeks to qualify to enter the randomized withdrawal phase of the study.

In the double-blind withdrawal phase of the study, “responders” from Part 1 and Part 2 of the open-label phase will be randomized in a 1:1 ratio to either continue tofacitinib or start placebo. The primary endpoint of the study is time to sJIA flare in the double-blind phase. The double-blind withdrawal phase will continue until a sufficient number of flares are reported as described in Section 11.

The Sponsor will use external Centralized Coordinating Centers to review and confirm applicable real-time assessments of efficacy, including the Adapted JIA ACR 30/50 response, sJIA flare, and inactive disease status (JIA-ACR). The Coordinating Centers will also monitor and offer recommendations on corticosteroid tapering of study participants. Refer to [Section 8.1.12](#) for details on the coordinating centers. The Centralized Coordinating Centers will be blinded to study drug assignment in the double-blind withdrawal phase of the study.

All subjects participating in this study, including those who discontinued in the open-label or double-blind phase, will have the option, if eligible (based on inclusion and exclusion criteria), of enrolling in the tofacitinib JIA long-term extension study (A3921145) after completion of this study.

[figure not shown]
Subjects who flare in the double-blind withdrawal phase will be given the opportunity to participate in A3921145 and be treated with open-label tofacitinib. Subjects who achieve ACR clinical remission (ie, maintain JIA ACR inactive disease during 24 consecutive weeks) will complete their participation in A3921165 and be given the opportunity to enter A3921145.

Subjects who discontinue Investigational Product in the double-blind phase and who do not enter A3921145 will continue in A3921165 for follow up of efficacy and safety endpoints. Subjects will be required to perform all scheduled visits until Week 52 after randomization or until the study concludes, whichever comes first. Subjects should receive standard-of-care treatment in accordance with local treatment guidelines.

Subjects who discontinue the study in the Open-Label Phase and do not enter A3921145, will be required to perform a follow-up visit 28 days after the last dose of study treatment.

A schematic of the study design is shown below:

Figure 2. Study Design

a Subjects <40 kg will receive an equivalent weight-based lower dose of tofacitinib 5 mg BID.

b CS Tapering is only required for subjects treated with CS >0.2 mg/kg/day oral prednisone (or equivalent). During the active CS tapering period in Part 2 subjects must maintain an Adapted JIA ACR 50 response.

c aJIA: Adapted JIA.

d Subjects who discontinue Investigational Product in the randomized withdrawal phase continue in study until week 52 after randomization, or until the study concludes, whichever comes first.

e Subjects who discontinue the study in the open-label phase and do not enter A3921145 within 4 weeks, will be required to perform a follow-up visit 28 days after the last dose of Investigational Product.

3.2. Open-label Phase: Variable Duration of 12 to 40 Weeks

The open-label active treatment period will consist of two parts:

3.2.1. Open-label Phase, Part 1: Treatment with Tofacitinib while on Stable Background Therapy

Part 1 of the open-label active treatment phase is designed to identify tofacitinib-treated subjects who are able to achieve and maintain an Adapted JIA ACR 30 response for at least 4 weeks while continuing on the stable CS dose identified during the screening period prior to treatment with tofacitinib.

All subjects ≥ 40 kg will receive tofacitinib 5 mg BID oral tablets; however, subjects who cannot swallow oral tablets and all subjects <40 kg will receive a weight-based dose of tofacitinib oral solution (1 mg/mL) BID with a maximum dose of tofacitinib 5 mg BID. The 5 mg BID dose of tofacitinib will be evaluated in a staggered fashion (cohorts of 7 subjects followed by safety review, as described under “Dose Selection” in [Section 3.4](#).

Clinical assessments, including laboratory testing, will be performed at Baseline (Day 1) prior to the start of tofacitinib treatment, on Day 3, Day 7, Day 14, Week 4, and thereafter on a monthly basis.

If subjects are using CS treatment at study start, doses must be stable and ≤ 1.0 mg/kg/day up to 30 mg/day oral prednisone (or equivalent), in the last week before the first study drug dose (Day 1) and remain stable for the full duration of the Open-label Phase Part 1. Subjects who are not taking CS or are not required to taper CS dosing (subjects taking doses of corticosteroids ≤ 0.2 mg/kg/day) must be able to maintain an Adapted JIA ACR 30 response for at least 4 weeks in the Open-label Phase Part 1 will be allowed to proceed to Part 2 of the Open-label Phase. CS doses >0.2 mg/kg/day must be tapered in Part 2 of the study. Before CS tapering can start in the Open-label Phase Part 2, subjects will be required to achieve an Adapted ACR 50 response in the Open-label Phase Part 1 in addition to maintaining an Adapted ACR 30 response for 4 weeks. The duration of the Open-Label Phase Part 1 for each subject is variable but will be no longer than 16 weeks.

Adapted JIA ACR 30 Response/Adapted JIA ACR 50 Response are defined as absence of fever due to sJIA (temperature $\leq 38^\circ$ C/ 100.4° F) in the preceding 7 days along with an improvement of at least 30% / 50% from baseline (Day 1 of study drug before first tofacitinib administration) in at least 3 of the 6 JIA core components, with worsening of $\geq 30\%$ / $\geq 50\%$ in no more than 1 of the remaining components, which include:

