3.2.2. Open-label Phase, Part 2: Treatment with Tofacitinib while Tapering Corticosteroids

Part 2 of the open-label active treatment phase serves to taper CSs in subjects receiving CS doses >0.2 mg/kg/day to a target range as outlined in Table 1. Subjects will have study visits on a monthly basis in Part 2.

Subjects who are treated with stable oral prednisone (or equivalent) doses ≤ 0.2 mg/kg/day who are able to maintain an Adapted JIA ACR 30 response for 4 weeks in Part 1 are allowed to skip Part 2 and be randomized in the Double-Blind Withdrawal Phase of the study (12-week minimum tofacitinib treatment duration in the Open-Label Phase is required).

The time period of Part 2 is variable, but no longer than 24 weeks, and CS tapering will only be allowed in the first 20 weeks. A subject must be on the final tapered CS dose on or before the day after the week 20 visit in Open-label Part 2. CS tapering in the Open-label Phase Part 2 can continue as long as an Adapted JIA ACR 50 response is maintained. After CS tapering to the target range (Table 1), or lower (Table 2), a subject must remain on a stable tapered CS dose and maintain an Adapted JIA ACR 30 response (minimum) for at least 4 weeks before randomization to the double-blind withdrawal phase. Subjects taking CS doses >0.2 mg/kg/day who fail to achieve an Adapted ACR 50 response during Part 2 of the Open-label phase of the study will be discontinued from the study and will not be randomized into the double-blind phase of the study.

The minimum total duration of treatment with a stable dose of tofacitinib for subjects completing Open-label Phase Parts 1 and 2 must be 12 weeks to qualify to enter the randomized withdrawal phase of the study.

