3.2.2.2. Two Corticosteroid Tapering Failures are Allowed

CS tapering can continue as long as:

Between study visits the subject does not report any sJIA associated fever or flares according to the investigator's judgment.

The subject maintains an Adapted JIA ACR 50 response at time of site visits.

CS tapering failure is defined as loss of Adapted JIA ACR 50 response. Subjects will be allowed to fail the CS tapering criteria twice in Part 2. If after 2 tapering failures the subject fails to taper CS a third time, they will be discontinued from the study and offered the possibility to enter the A3921145 study if eligible.

If a subject has a first CS tapering failure, continuation in the study will be allowed, but the steroid dose will be increased to the level of the previous visit, or higher, at the judgment of the investigator. The increased CS dose cannot exceed 1.0 mg/kg/day up to 30 mg/day of oral prednisone (or equivalent). This increased CS dose will be maintained for at least 2 weeks. Subsequent attempts of steroid tapering may occur only if the subject has re-achieved an Adapted JIA ACR 50 response. If after 2 weeks, the subject does not re-achieve an Adapted JIA ACR 50 response this will be considered a second tapering failure. If the subject fails a third CS tapering attempt they will be discontinued from the study.

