8.1.7. Adapted ACR 30 Pediatric Criteria: JIA Core Set Variables and Response

The disease activity of sJIA will be measured using an adaptation of the JIA American College of Rheumatology (ACR) 30 response. The Adapted JIA ACR 30 Response criteria include the components of the pediatric ACR core set along with the absence of fever due to sJIA in the preceding 7 days.¹⁴ Fever is defined as temperature $>38^{\circ}$ C (100.4° F). The Adapted JIA ACR 30, 50, 70, 90, 100 response is defined as the absence of fever due to sJIA in the preceding 7 days along with at least 3 out of 6 JIA core set variables improved $\geq 30\%$, 50%, 70%, 90%, 100%, respectively, with no more than 1 out of 6 JIA core set variables worsened by $\geq 30\%$, which include:

- Number of joints with active arthritis;
- Number of joints with limited range of motion;
- Physician global evaluation of disease activity;
- Parent/ legal guardian/Child evaluation of overall well-being;
- Functional ability (CHAQ Disability Index);

- ESR.*

The Adapted JIA ACR 30, 50, 70, 90, 100 response rate will be determined at every visit from Day 7 onward based on the investigator's and parent/legal guardian's assessment of components of the JIA core set variables.

*For "real-time" assessment of the Adapted JIA ACR 30 Response during a study visit the subject's ESR will be used to determine the percent change in inflammation biomarker. CRP may be used for analysis of other related endpoints (details will be provided in the Statistical Analysis Plan [SAP]).

At the end of the open-label phase, only subjects who were able to maintain an Adapted JIA ACR 30 response for at least 4 weeks in accordance with the protocol requirements of [Section 3.2](#), will be randomized into the double-blind, placebo-controlled phase.

Achievement and maintenance of an Adapted JIA ACR 30 response in the open-label phase will need be confirmed by the Centralized Coordinating Center. Investigators must enter this confirmation in the eCRF at every study visit from the Day 7 visit onward.

Following confirmation, the investigator site will randomize the subject utilizing the Sponsor's Interactive Response Technology (IRT) system (see [Section 5.1](#)).

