#### **Appendix 3.4. The Adapted JIA ACR30-50-70-90-100 Response**

The disease activity of sJIA will be measured using an adaptation of the JIA American College of Rheumatology (ACR) 30 response ([Giannini 1997](#)). The Adapted JIA ACR30 Response criteria include the components of the pediatric ACR core set ([Appendix 3.1](#)) along with the absence of fever, defined as temperature  $\leq 38^{\circ}\text{C}/100.4^{\circ}\text{F}$  in the preceding 7 days. The Adapted JIA ACR30, 50, 70, 90, 100 response is defined as the absence of fever due to sJIA (oral temperature  $\leq 38^{\circ}\text{C}/100.4^{\circ}\text{F}$ ) in the preceding 7 days along with at least 3 out of 6 JIA core set variables improved  $\geq 30\%$ , 50%, 70%, 90%, 100%, respectively, with no more

than 1 out of 6 JIA core set variables worsened by >30%. Only ESR will be used to calculate Adapted JIA ACR responses.

The Adapted JIA ACR30, 50, 70, 90, 100 response will be determined at every visit from Day 7 onward based on the investigator's and parent/legal guardian's assessment of components of the JIA core set variables.

If the value in any of the components at a timepoint is missing, the component variables that are not missing will be used to determine the response status. As a general principle, if there are sufficient non-missing components to determine whether the JIA ACR endpoint is a response or non-response, then JIA ACR endpoint is not missing, else if the available non-missing components are not sufficient to determine the response status of JIA ACR endpoint then it is considered missing.

In order to avoid numerical difficulty, if the baseline value of any component is equal to 0, the following algorithm will be used in evaluating the percent change from baseline:

1. If change from baseline is also equal to 0, then percent change from baseline is set to be 0%;
2. If change from baseline is > 0, then percent change from baseline is set to be 999999%.

These percentages will be used to derive the JIA ACR endpoints. Change from baseline cannot be < 0 since none of the components should have negative value.

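### The worsening limit in the Adapted JIA ACR response is written three ways, so one visit can count as ACR 50 response or as loss of it, depending on the section used

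*Protocol*

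**What the plan says.** Three current passages define the response.

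- **Protocol 3.2.1** defines ACR 30 and ACR 50 together and allows worsening of ≥30% (for ACR 30) or ≥50% (for ACR 50) "in no more than 1 of the remaining components". The limit therefore rises with the response level.
- **Protocol 8.1.7** covers ACR 30 to 100, "with no more than 1 out of 6 JIA core set variables worsened by" 30% or more. The limit is the same at every level.
- **SAP Appendix 3.4** covers the same five levels but allows no more "than 1 out of 6 JIA core set variables worsened by >30" per cent. A worsening of exactly 30% does not count against the child.

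ACR 50 controls the steroid taper at three points. Before a taper starts, "subjects will be required to achieve an Adapted ACR 50 response in the Open-label Phase Part 1" (3.2.1). During Part 2, "CS tapering in the Open-label Phase Part 2 can continue as long as an Adapted JIA ACR 50 response is maintained" (3.2.2). Protocol 3.2.2.2 then states that "CS tapering failure is defined as loss of Adapted JIA ACR 50 response", and a third failure leads to discontinuation.

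The coordinating center confirms ACR 30 and ACR 50 in real time (Protocol 8.1.12), but that section gives no worsening limit. The sponsor derives the analysed ACR responses separately by program; only double-blind flare keeps the coordinating center's result (SAP 5.2 and 5.3.2.1).

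**The concern.** The two protocol sections define ACR 50 differently, and both bear on the taper. Section 3.2.1 contains the rule for starting a taper. Section 8.1.7 describes the assessment and the coordinating center's confirmation of ACR response, and itself points back to Section 3.2. A site or the coordinating center could follow either in good faith and reach opposite conclusions at the same visit.

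The SAP adds a third limit for the analysed responses. ACR 30/50/70/90/100 are secondary endpoints in both phases, and ACR 30/50/70 are also analysed by subgroup (SAP 6.4). If the limits are not aligned, the analysed ACR 50 need not be the ACR 50 used to manage the child's taper.

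**Working it through.** The plan gives no figure to reproduce here, so the check is to apply the three written rules to the same children.

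**Rule.** No fever due to sJIA; at least 3 of 6 components improved by the level (30% or 50%); at most 1 component worsened to the limit. The limits are ≥ the level for ACR 30 and ACR 50 (3.2.1), ≥30% (8.1.7) and >30% (SAP).

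**Hypothetical children.** Three components have improved by 60%; the other three change as shown (+ is worsening).

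| Other three | ACR 50: 3.2.1 / 8.1.7 / SAP | ACR 30: 3.2.1 / 8.1.7 / SAP |
|---|---|---|
| +40, 0, 0 | yes / yes / yes | yes / yes / yes |
| +40, +40, 0 | **yes / no / no** | no / no / no |
| +40, +60, 0 | **yes / no / no** | no / no / no |
| +30, +30, 0 | **yes / no / yes** | no / no / **yes** |
| +30, +40, 0 | **yes / no / yes** | no / no / **yes** |
| +60, +60, 0 | no / no / no | no / no / no |

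Rows 2 and 3 show the main conflict. They also show that under 3.2.1 the levels are not nested: the child meets ACR 50 and fails ACR 30.

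**Protocol 8.1.7 against the SAP.** These differ only when at least two components have worsened by 30% or more and no more than one of them has worsened by more than 30%. At least one must therefore sit at exactly 30%. Such values are attainable: 10 to 13 joints (13/10 = 1.30), a global score of 5.0 to 6.5 (6.5/5.0 = 1.30), CHAQ disability index 1.25 to 1.625 (1.625/1.25 = 1.30), and ESR 40 to 52 (52/40 = 1.30). One such tie alone changes nothing, because every version allows one worsened component (row 1 shows the same allowance).

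**Illustrative size of the conflict between 3.2.1 and a 30% limit.** The documents give no rates, so these are assumptions. Take a child with exactly three components improved by at least 50%. Let each of the other three independently worsen by 30% to under 50% with probability q, and by 50% or more with probability r. With s = q + r, the share who are ACR 50 responders under 3.2.1 but not under a 30% limit is

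[(1−r)³ + 3r(1−r)²] − [(1−s)³ + 3s(1−s)²]

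| q | r | First bracket | Second bracket | Share |
|---|---|---|---|---|
| 0.02 | 0.02 | 0.9988 | 0.9953 | 0.35% |
| 0.05 | 0.05 | 0.9927 | 0.9720 | 2.1% |
| 0.10 | 0.10 | 0.9720 | 0.8960 | 7.6% |
| 0.20 | 0.10 | 0.9720 | 0.7840 | 18.8% |

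**Weight of one child.** Protocol 10.1.1 expects 54 randomised 1:1, so 54/2 = 27 per arm. One child classified differently moves an arm's response rate by 1/27 = 3.7 percentage points.

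**The case against.** The strongest reply is that the SAP may modify the protocol's plans (Protocol 10, SAP 2), so the SAP limit governs the analysed responses, and that the coordinating center may already apply 8.1.7 throughout. If so, taper decisions and analysis differ only at exact 30% ties. That narrows the problem but does not remove it. The SAP's authority over analyses cannot settle a conflict between two protocol sections on taper conduct. Protocol 8.1.12 refers to validated criteria and a separate manual, not to either section. The SAP version history names no change to this limit, and the SAP's own flare rule (Appendix 3.3) counts worsening of 30% or more, so nothing shows that >30% was deliberate.

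The documents do not support several stronger readings that a reader might infer:

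- *The denominators conflict* (remaining components against all six). They do not. A component that improved cannot also have worsened, so every worsened component is among the remaining ones and the counts always agree.
- *Coordinating center and analysis can disagree on ACR 50 in both directions.* Not under any single coordinating-center rule. With 3.2.1, only responder at the center and non-responder in the SAP is possible. With 8.1.7, only the opposite is possible, and only at ties.
- *The limit directly decides who is randomised.* Starting a taper also requires ACR 30 maintained for 4 weeks, and randomisation requires ACR 30 for at least 4 weeks. The child with two components worsened by 40% fails ACR 30 under all three versions and cannot be randomised in that state.
- *The primary result is affected through its definition.* Flare has its own criteria and uses the coordinating center's result. Analysed taper success is defined by ACR 30, and open-label ACR results are descriptive.

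**Conclusion.** The conflict is real and lies in current text, but it is minor. Protocol 3.2.1 and 8.1.7 give different ACR 50 definitions, and the practical exposure is in Part 2: whether a taper continues and whether a taper failure is counted. Randomisation is affected only indirectly, through accumulated failures. Between 8.1.7 and the SAP the difference is confined to exact 30% ties with a second component worsened by at least 30%; at such ties it reaches ACR 30 as well as ACR 50.

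How many children are affected is unknown. The 0.35% to 18.8% range rests wholly on assumed worsening rates and on independence, and applies only to children with exactly three components improved by at least 50%. The wider gap between taper decisions and analysis also depends on the coordinating center applying 3.2.1 as written, which the documents neither confirm nor exclude.

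**What to change.** 1. Reconcile Protocol 3.2.1 and 8.1.7 so that the protocol contains one ACR 50 definition. Which limit should govern tapering is a clinical decision for the sponsor, and this review does not propose one.
2. State in Protocol 8.1.12 which definition the coordinating center applies in real time.
3. Align the inequality in SAP Appendix 3.4 with the reconciled protocol definition, so that the analysed ACR 30/50/70/90/100 responses are the protocol's endpoint.

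The cost is wording in the two protocol definitions and the SAP appendix, one sentence on the coordinating center, and one condition in the derivation program. No data collection changes.

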3.2.2. Open-label Phase, Part 2: Treatment with Tofacitinib while Tapering Corticosteroids

Part 2 of the open-label active treatment phase serves to taper CSs in subjects receiving CS doses >0.2 mg/kg/day to a target range as outlined in Table 1. Subjects will have study visits on a monthly basis in Part 2.

Subjects who are treated with stable oral prednisone (or equivalent) doses ≤ 0.2 mg/kg/day who are able to maintain an Adapted JIA ACR 30 response for 4 weeks in Part 1 are allowed to skip Part 2 and be randomized in the Double-Blind Withdrawal Phase of the study (12-week minimum tofacitinib treatment duration in the Open-Label Phase is required).

The time period of Part 2 is variable, but no longer than 24 weeks, and CS tapering will only be allowed in the first 20 weeks. A subject must be on the final tapered CS dose on or before the day after the week 20 visit in Open-label Part 2. CS tapering in the Open-label Phase Part 2 can continue as long as an Adapted JIA ACR 50 response is maintained. After CS tapering to the target range (Table 1), or lower (Table 2), a subject must remain on a stable tapered CS dose and maintain an Adapted JIA ACR 30 response (minimum) for at least 4 weeks before randomization to the double-blind withdrawal phase. Subjects taking CS doses >0.2 mg/kg/day who fail to achieve an Adapted ACR 50 response during Part 2 of the Open-label phase of the study will be discontinued from the study and will not be randomized into the double-blind phase of the study.

The minimum total duration of treatment with a stable dose of tofacitinib for subjects completing Open-label Phase Parts 1 and 2 must be 12 weeks to qualify to enter the randomized withdrawal phase of the study.

